6.6 Removal of Patients from Protocol Therapy

In case a patient decides to prematurely discontinue protocol therapy ("refuses treatment"), the patient should be asked if she or he may still be contacted for further scheduled study assessments. The outcome of that discussion should be documented in the medical record. Patients may also be removed from the study at any time per PI discretion due to unexpected reactions, lack of study compliance or for study closure.

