6.4 Definition of Dose Limiting Toxicity

A dose-limiting toxicity is defined as all Grade 3 or above acute toxicities attributed to the treatment under study. The accrual will be halted if the number of patients with dose-limiting toxicities equals to or exceeds a rate of 30%.

6.5 **Duration of Follow Up**

All patients will be followed for up to 5 years after radiation, or until death, whichever occurs first, after removal from study treatment for determination of study endpoints. Patients removed from study treatment for unacceptable adverse events (AEs) will be followed for resolution or stabilization of the AEs. All patients (including those withdrawn for AEs) should be followed after removal from study treatment as stipulated in the protocol.

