6.8 Study Withdrawal

If a patient decides to withdraw from the study (and not just from protocol therapy) an effort should be made to complete and report study assessments as thoroughly as possible. At the time of withdrawal, the investigator should attempt to establish as completely as possible the reason for the study withdrawal.

- The patient should be asked if they are willing to allow for the abstraction of relevant information from their medical record in order to meet the long term follow up (e.g., biochemical control or survival) objectives outlined in the protocol.
- A complete final evaluation at the time of the patient's study withdrawal should be obtained with an explanation of why the patient is withdrawing from the study.
- If the patient is noncompliant and does not return for an end of study follow up assessment, this should be documented in the case report form (CRF).
- If the reason for removal of a patient from the study is an adverse event, the principal specific event will be recorded on the CRF.

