8.5 Early Termination Visit

Subjects may withdraw voluntarily from participation in the study at any time. Subjects may also withdraw voluntarily from receiving the study intervention for any reason. No specific evaluations will be required in the setting of early termination.

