8.6 Assessment of Safety

All patients who received treatment (i.e. radiation) will be evaluated for toxicity at specified time points throughout the study; toxicity will be measured according to CTCAE version 5.0.

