We denote p the probability that a patient experiences a late grade 2+ GU/GI toxicity. We want p to be small enough to claim the new imaging strategy (PSMA/PET-mpMRI) as feasible with no greater late toxicity. Specifically, the null and alternative hypotheses are:

$H_0: p \ge 0.30 \ vs \ H_1: p \le 0.15$

That is, we accept the claim that the new strategy is safe if the observed toxicity rate is not too high, and hope to reject the claim (H0) with sufficient power when the true toxicity rate is about 20%. With a sample size of 38, we reach 80% power to reject (if we observe ≤ 7 cases with late toxicity) the null hypothesis (H0) at alpha = 0.1. To account for 10% loss follow-up, we will enroll 42 patients to ensure 38 evaluable patients.

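### Men removed from the study by the PI for unexpected reactions have no stated follow-up and no stated place in the primary toxicity count, which can tilt the test towards declaring safety

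*Combined protocol and SAP*

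**What the plan says.** **Removal.** Section 6.6 is headed as removal from protocol therapy, but its last sentence concerns removal from the study: "Patients may also be removed from the study at any time per PI discretion due to unexpected reactions, lack of study compliance". Study closure is the remaining reason listed. Nothing in 6.6 says what data are collected after the PI removes a man.

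**Follow-up.** Section 6.5 covers men who come off study treatment: "All patients will be followed for up to 5 years after radiation, or until death, whichever occurs first, after removal from study treatment", and "All patients (including those withdrawn for AEs) should be followed after removal from study treatment as stipulated in the protocol". Section 8.6 adds: "All patients who received treatment (i.e. radiation) will be evaluated for toxicity at specified time points throughout the study".

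**Exit data.** Section 6.8, which opens with the patient's own decision to withdraw, asks for a complete final evaluation. It also provides: "If the reason for removal of a patient from the study is an adverse event, the principal specific event will be recorded". Its record abstraction is "in order to meet the long term follow up (e.g., biochemical control or survival) objectives outlined in the protocol", with no mention of toxicity. Section 8.5 states: "No specific evaluations will be required in the setting of early termination".

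**Analysis.** Section 10.1 rejects the null hypothesis of a toxicity rate of 0.30 or more if 7 or fewer of 38 men have late toxicity, and sizes the trial thus: "To account for 10% loss follow-up, we will enroll 42 patients to ensure 38 evaluable patients". Section 10.2 equates drop-out with being non-evaluable. Neither section defines evaluable or gives a rule for a man who leaves before month 12. Section 10.3 carries the same plan to the available data if the study ends early.

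**The concern.** The primary objective is safety, and a low event count is the favourable result. If a man leaves because of a reaction, his absence is related to the outcome being counted. If he is then treated as non-evaluable, he drops out of both numerator and denominator, and the remaining men look healthier than the treated group. The error runs in one direction: it makes it easier to reject the null hypothesis of excessive toxicity. The 10% allowance in Section 10.1 keeps up the number analysed but does nothing about which men are missing.

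**Working it through.** **Inputs (Section 10.1).** Null rate 0.30, alternative 0.15, 38 evaluable men, success at 7 or fewer events, alpha 0.10, stated power 80%, 42 enrolled.

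**The plan's own figures.** With X the number of events, exact binomial:
- Power: P(X ≤ 7 | n = 38, p = 0.15) = 0.7986, which agrees with 80%.
- Type I error: P(X ≤ 7 | n = 38, p = 0.30) = 0.0795, within 0.10. A cut-off of 8 would give 0.1518, so 7 is the right cut-off.
- Enrolment: 38 × 1.10 = 41.8, rounded up to 42.

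**Illustration 1: k men with toxicity removed and not counted.** The number k is an assumption. With 38 + k men treated and 38 left for analysis, the trial passes when the true event count is at most 7 + k. The chance of falsely declaring safety is P(Bin(38 + k, 0.30) ≤ 7 + k):

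| k | Treated | True events still passing | Chance of falsely declaring safety |
|---|---|---|---|
| 0 | 38 | 7 | 0.079 |
| 1 | 39 | 8 | 0.130 |
| 2 | 40 | 9 | 0.196 |
| 3 | 41 | 10 | 0.275 |
| 4 | 42 | 11 | 0.363 |

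At k = 4, an observed 7/38 (18.4%) stands for a true 11/42 (26.2%).

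**Illustration 2: a share m of men with toxicity removed.** Here m is an assumption, all men without toxicity stay, and 38 men are analysed. The rate seen among those left is q = 0.30(1 − m)/(1 − 0.30m), and the chance of falsely declaring safety is P(X ≤ 7 | n = 38, q):
- m = 5%: q = 0.289, chance 0.102
- m = 10%: q = 0.278, chance 0.131
- m = 20%: q = 0.255, chance 0.209
- m = 30%: q = 0.231, chance 0.323

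Under either construction a small selective loss takes the error above the stated 0.10: one man, or about 5% of those with toxicity.

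**The text on a man removed by the PI.** Section 6.5 is written for men off treatment and 6.6 for men off study, so 6.5 does not clearly reach him. Section 6.8 records the event that led to his removal, but its final evaluation is framed around patient withdrawal, and 8.5 requires no evaluation at early termination. No section says whether his recorded event enters the primary count, and toxicity arising after he leaves might never be collected.

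**The case against.** A reader might infer that Section 6.6 flatly contradicts Section 6.5. It does not: one concerns leaving the study, the other leaving treatment. The two are unreconciled, which is a lesser fault.

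A reader might also equate unexpected reactions with the primary endpoint. Section 9.1.3 calls an event unexpected when its specificity or severity departs from the product information. Late GU and GI toxicity is anticipated here, and Section 10.1 tabulates it from earlier studies. Late toxicity also starts more than 3 months out, when a radiation course of about 2 months is over. So only some endpoint events, unusual in kind or severity, are likely to prompt removal. That stands, although the clause applies at any time.

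There are safeguards. Section 6.8 puts the triggering event on the CRF, Section 8.4 follows ongoing grade 2 or higher events and SAEs until they resolve or are judged irreversible, and Sections 9.2 and 9.3 run event recording through 5 years. No passage says that a man with a recorded toxicity is non-evaluable. This also stands: exclusion is something the plan permits, not something it directs. But no passage says that he is counted, either.

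Finally, the 10% allowance is for loss to follow-up, not for PI removal. Four toxic removals would use all of it and would be about a third of the 12.6 men expected to have toxicity at a 30% rate (42 × 0.30). The 36.3% is an extreme, not an estimate.

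**Conclusion.** The concern holds as a gap. The plan allows men to leave the study for a reason that can overlap with the primary outcome, does not secure their toxicity data, and does not say how they are counted. Any resulting bias favours declaring safety.

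Its size is unknown. The documents give no removal rate, and the range from 7.9% (none lost) through 13.0% (one) to 36.3% (four) rests on assumed numbers, a true rate of 30% and complete follow-up of everyone else. It would be wrong to infer that such removals have happened, or that the false-safety risk is 36%.

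The documents do not support treating this as critical. Amendment 6 supports early closure for low accrual, so the 38-man rule may never be applied. The gap still matters because Section 10.3 uses the same analysis on the available data, and study closure is itself a reason for removal in Section 6.6.

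One related matter must be settled separately: Section 4.1 sets the primary endpoint at grade 3 or higher, while the test in Section 10.1 uses grade 2 or higher. What counts as a qualifying toxicity depends on the answer.

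**What to change.** 1. **Sections 6.5, 6.6, 6.8 and 8.5.** Reconcile them so that toxicity data collection continues after a man leaves therapy or is removed by the PI, unless he declines. State one requirement for the evaluation at exit. This concerns data only and sets no rule on who may be removed.
2. **Sections 10.1 and 10.3.** Define the primary analysis set as all irradiated men who have either 12-month data or a qualifying late GU/GI toxicity before exit, and count the latter as events. Say whether a late event that resolves before month 12 counts for men who stay, so that both groups are scored alike. If the number analysed is not 38, take as cut-off the largest count whose null probability is at most 0.10. Exact binomial gives 7 for 37 to 40 men and 8 for 41 or 42.
3. **Section 10.3.** Add a sensitivity analysis that counts treated men without 12-month data as events.
4. **Section 6.8.** Name late GU/GI toxicity among the data to abstract from the record.

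The cost is a few sentences and one extra table, and items 2 and 3 can be applied to data already collected. The downside is that the reported toxicity rate may be slightly less favourable. The analysis set in item 2 keeps early leavers with an event but not those without, so it leans slightly towards a higher rate, which is the cautious direction for a safety claim.

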6.7 Subjects Lost to Follow-Up

Subject will be considered lost to follow-up if he fails to return for three scheduled visits and is unable to be contacted by the study site staff.

The following actions must be taken if a subject fails to return to the clinic for a required study visit:

• The site will attempt to contact the subject and reschedule the missed visit and counsel the subject on the importance of maintaining the

assigned visit schedule and ascertain if the participant wishes to and/or should continue in the study.

• Before a subject is deemed lost to follow-up, the investigator or designee will make every effort to regain contact with the subject (where possible, 3 telephone calls and, if necessary, a certified letter to the participant's last known mailing address or local equivalent methods). These contact attempts should be documented in the subject's medical record or study file.

Should the subject continue to be unreachable, he or she will be considered to have withdrawn from the study with a primary reason of lost to follow-up.

6.8 Study Withdrawal

If a patient decides to withdraw from the study (and not just from protocol therapy) an effort should be made to complete and report study assessments as thoroughly as possible. At the time of withdrawal, the investigator should attempt to establish as completely as possible the reason for the study withdrawal.

- The patient should be asked if they are willing to allow for the abstraction of relevant information from their medical record in order to meet the long term follow up (e.g., biochemical control or survival) objectives outlined in the protocol.
- A complete final evaluation at the time of the patient's study withdrawal should be obtained with an explanation of why the patient is withdrawing from the study.
- If the patient is noncompliant and does not return for an end of study follow up assessment, this should be documented in the case report form (CRF).
- If the reason for removal of a patient from the study is an adverse event, the principal specific event will be recorded on the CRF.

7.0 EVALUATIONS AND ASSESSMENTS

7.1 Clinical Assessments

Clinical assessments will be performed as outlined in the Time and Events Table in Section 8.1.

7.1.1 Demographics

Demographic information (date of birth, gender, race) will be recorded at screening.

7.1.2 Medical History

Relevant medical history, including history of current disease, other pertinent respiratory history (e.g., tobacco use), and information regarding underlying diseases will be recorded at screening and a focused medical history on symptoms/toxicity will be performed thereafter.

7.1.3 Physical Examination

A complete physical examination including height (at screening only), weight, performance status (ECOG) and vital signs (e.g., temperature, heart rate, respiratory rate, pulse oximetry and blood pressure) will be performed by either the investigator or a sub-investigator who is a physician at screening and the first study visit.

Qualified staff (MD, NP, RN, and PA) may complete the abbreviated physical exam at all other visits.

New abnormal physical exam findings must be documented and will be followed by a physician or other qualified staff at the next scheduled visit.

7.1.4 Adverse Events

Events should be assessed per NCI-CTCAE criteria 5.0. Information regarding occurrence of adverse events will be captured throughout the study. Duration (start and stop dates), severity/grade, outcome, treatment and relation to study treatment will be recorded in the case report form. A dose-limiting toxicity is defined as all Grade 3 or above acute toxicities attributed to the treatment under study. The accrual will be halted if the number of patients with dose-limiting toxicities equals to or exceeds a rate of 30%.

7.1.5 Disease Assessment

Patients' disease will be assessed with prostate-specific antigen (PSA) test draws. PSA will be obtained at within three months prior to study enrollment and then at each follow up (1, 3, 6, 9, 12, 18, 24, 30, 36, 42, 48, 54, and 60 months post treatment).

7.2 Clinical Laboratory Assessments

7.2.1 Hematology

Blood will be obtained at screening and sent to the clinical site hematology lab for a complete blood count (hemoglobin, hematocrit, red blood cell count, white blood cell count, white blood cell differential, and platelet count), coagulations (International Normalized Ratio (INR) or prothrombin time (PT) and partial thromboplastin time (PTT)).

7.2.2 Blood Chemistry Profile

Blood will be obtained at screening and sent to the clinical site chemistry lab for a complete metabolic panel (serum sodium, potassium, chloride, bicarbonate, glucose, BUN, creatinine, aspartate aminotransferase (AST/SGOT), alanine aminotransferase (ALT/SGPT), alkaline phosphatase, total bilirubin, direct bilirubin, gamma-glutamyl transferase (GGT), albumin and LDH).

7.2.3 Pathology

At time of fiducial markers placement, GTVs (i.e. DILs) will be biopsied by the treating radiation oncologist and a urologist. Two cores will be taken per GTV and placed in buffered formalin containers. This is a research only biopsy and will be used to evaluate the sensitivity and specificity of PSMA-PET/MRI vs PSMA-PET/CT. It will not require any additional visits or cost for the subject. These samples will be collected and accessioned with coded identifiers by the Tissue Procurement Facility (TPF). Specimen processing, embedding and histologic sectioning will be performed by the Translational Pathology Laboratory (TPL) and slides interpreted by the collaborating pathologist.

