Regarding nodal radiation, there are three published large randomized controlled trials looking at the role of pelvic nodal irradiation in nonmetastatic prostate cancer which have proved inconclusive.^{11–13} More recently, a randomized study conducted at a single institution in India (POP-RT, Murthy et al., JCO 2021) demonstrated improvements in biochemical failure free survival, disease free survival, and distant metastasis free survival with the addition of pelvic radiotherapy in patients with a nomogram-predicted risk of occult nodal metastasis exceeding 20%.¹⁴ There are two more trials currently underway (NCT01368588; PEACE 2 - GETUG - AFU 23) with estimated primary completion dates in 2025-2027.^{15,16} Collectively, these studies demonstrate the clinical equipoise in this area (whether or not to include nodes in the treatment field), which has been an area of intense debate for at least two decades (Nguyen & D'Amico, JCO 2008; Roach, JCO 2008).^{17,18}

Regarding defining intraprostatic lesions, ⁶⁸Ga-PSMA-PET alone has not been perfect. One meta-analysis found in seven studies that PSMA-expressing lesions were identified in only 203 of 273 patients (74%).¹⁹ However, this number appears to be confounded by lymph node detection rates. When looking at PSMA-PET defined DILs alone, the detection rates could be over 95%,²⁰ and may be even higher in high-risk disease which have greater PSMA-PET avidity.²¹ Three separate studies have shown that MRI and PSMA can deliver complimentary information on the localization of DILs.^{22–24} Therefore, it is likely PSMA PET-MRI is advantageous to PSMA PET-CT alone in identifying DILs. In a slice-by-slice analysis with histopathology, the sensitivity for PSMA PET alone, mpMRI alone, and PSMA PET-MRI combined, was 75%, 70%, and 82%, respectively for prostate cancer tumor detection. The specificity was 87%, 82%, and 67%, respectively.²⁵ Others have also found PSMA-PET/MRI to be superior to multiparametric MRI alone in detecting prostate cancer.²⁶

The concept of biological-guided (e.g. with PET) dose escalation (e.g. to DILs) is not new,²⁷ but has never been done with in combination with SBRT-CK. A feasibility study such as the current study under investigation will be the first step to investigating this question. Based on other studies, know that dose escalation in prostate cancer improves progression free survival.^{28,29}

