3.3 Exploratory Objectives

4.0 STUDY ENDPOINTS

4.1 Primary

The planning criteria that will be used are the current standard of care and standard practice at UNC and includes defined treatment volumes with a prescribed dose while respecting the dose constraints to all organs at risk. The primary endpoint is grade 3+ late genitourinary toxicity and gastrointestinal toxicity as classified and graded according to the National Cancer Institute's Common Terminology Criteria for Adverse Events (CTCAE), version 5.0 at 12 months after radiation therapy.

- 4.2 Secondary
- 4.2.1 Grade 3+ acute and late genitourinary and gastrointestinal toxicity will be defined according to CTCAE, version 5.0 during radiation therapy and at 1, 3, 6, 9, 12, 18, 24, 30, 36, 42, 48, 54 and 60 months post radiotherapy. Additionally, this will be reported as a cumulative incidence over the entire 5-year course of the study.
- 4.2.2 Biochemical control will be defined according to the Phoenix criteria³³ (PSA rise of 2 ng/mL over nadir) at 2 and 5 years after radiation therapy.
- 4.2.3 Patient reported quality of life will be measured using the Expanded Prostate Cancer Index Composite (EPIC-26) and the Urinary Obstruction/Irritation scale of the validated Prostate Cancer Symptom Indices (PCSI). Patient reported quality of life will be measured before the start of radiation therapy at 1, 3, 6, 9, 12, 18, 24, 30, 36, 42, 48, 54, and 60 months post radiotherapy.
- 4.2.4 The total number of subjects enrolled on the study will be compared to the total number of screened subjects.
- 4.2.5 The feasibility of meeting dose constraints will be defined as the proportion of subjects who meet the following dose constraint criteria:
 - SBRT-CK boost dose prescription: 6.5Gy x 3
 - PTV: V19.5Gy > 95%
 - PTVmax > 150%, CI < 1.8
 - CTV: V19.5Gy > 99%
 - \circ DIL: V24.0Gy > 99%

- SBRT-CK boost dose constraints:
 - o Rectum
 - V21.1Gy< 5 %
 - V18.9Gy< 20 %
 - V17.5Gy<10 %
 - V16.2Gy< 40 %
 - V10.2Gy< 60 %
 - V9.3Gy< 40 %
 - V19.5Gy<1cc
 - Max<21.2Gy
 - Bladder
 - V21.1Gy< 5 %
 - V19.5y < 5 cc
 - V9.3Gy<40 %
 - Max<21.2Gy
 - Prostatic Urethra
 - V19.5Gy > 95%
 - V22Gy < 0.03cc
 - Membranous Urethra
 - V18 Gy < 50%
 - Large bowel
 - V15Gy<1cc
 - Small bowel
 - V15Gy<1cc
 - Penile bulb
 - V15Gy< 3cc

4.2.6 Performance of PSMA-PET/MRI to PSMA PET/CT as defined as:

- Rate of identification and delineation of DIL (e.g. sensitivity and specificity)

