 - Compared to a gold standard of image-guided prostate biopsy
- Rate of identification of positive pelvic nodes
- Rate of identification of distant metastatic disease in the pelvis
- 4.2.7 Rate of identification of positive pelvic nodes by PSMA-PET and therefore the proportion of patients who have pelvic nodes included in the radiation field.

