6.1.1.1.3 SBRT with CyberKnife

- 1. SBRT with the use of CyberKnife will occur roughly 6 weeks after initiation of EBRT. Standard departmental protocol will be followed for CK-SBRT preparation. Patients with seminal vesicle involvement are eligible and seminal vesicles will be covered with CK-SBRT only as clinical indicated.
- 2. The fusion of the PSMA PET/mpMRI scans with the planning CT will be carried out in the treatment planning software; the fiducials will be used for soft tissue registration. Initially, the T2w MRI sequence will be registered with the planning CT by mutual information registration via fiducials. If necessary, manual adjustments may also be applied during image registration. The PSMA-PET and rest of the MRI and PET-CT scans will share the registration between the T2w MRI scan and planning CT.
- 3. The GTV-MRI will be outlined as a joint effort between a radiologist and the treating radiation oncologist on the basis of the PI-RADs v2 criteria.³⁴⁻³⁵ Additionally, the GTV-PET will be contoured again jointly between the radiologist and radiation oncologist by 30% of the SUVmax value.²⁴ This will be done by taking into account all additional information (including tumor localization in the diagnostic biopsy and physical exam [palpation]). An additional volume (GTV-union) is created from both GTVs.
- 4. The GTVs (i.e. DILs), will be biopsied as a joint effort between the treating radiation oncologist and a urologist. Two cores will be taken per GTV.
- 5. Contouring of the prostate, rectum, and urethral will be performed per UNC standard practice and SBRT with CyberKnife will be performed per UNC standard practice.

- 6. Per UNC standard practice, if the CT or the MRI imaging shows suspicious pelvic nodes, these will be included in the radiation treatment field. If the PSMA imaging alone shows suspicious pelvic nodes, a biopsy of the suspicious node will be offered, and upon confirmation, these may be included in the radiation treatment field.

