10.2 Sample Size and Accrual

Accrual will take place at UNC. The design as proposed in the above section leads to 80% power at an alpha level of 10%. Taking into account that the dominant intraprostatic lesion (DIL, image-identified tumor in the prostate) can be safely defined in around 75% of the patients, and assuming a 10% patient drop-out (nonevaluable) rate, we will plan to enroll 42 patients in order to achieve the primary objective of this study. Based on a previous study conducted with a similar population, we anticipate averaged accrual of 2 patients per month, corresponding to 21 months to enroll 42 patients out of which we can accrue the 38 evaluable patients for this study.

Sequential boundaries will be used to suspend the trial if excessive grade 4 toxicity of any type, attributed to the treatment under study, is seen. If the study reaches a stopping boundary, it may be terminated by the PI, or submitted to the Data and Safety Monitoring Committee with a description of the failures to date and a rationale for why the study should be continued.

The accrual will be halted if the number of grade 4 toxicities is equal to or exceeds b_n out of n patients with full toxicity follow-up (see table below). This is a Pocock-type stopping boundary that assumes that a grade 4 toxicity rate of 0.05 is acceptable. If the true grade 4 toxicity rate is equal to 0.05, the probability of crossing the boundary is 0.20.

Number of Patients, n 1	2	3	4	5	6	7	8	9	10
Boundary, b _n 1	2	2	2	2	2	2	2	2	2
Number of Patients, n 11	l 12	13	14	15	16	17	18	19	20
Boundary, b _n 3	3	3	3	3	3	3	3	3	3
Number of Patients, n 21	1 22	23	24	25	26	27	28	29	30
Boundary, b _n 3	3	4	4	4	4	4	4	4	4
Number of Patients, n 31	1 32	33	34	35	36	37	38	39	40
Boundary, b _n 4	4	4	4	4	5	5	5		

In addition, grade 3+ toxicity (DLT) will also be monitored. The accrual will be halted if the number of grade 3+ DLTs is equal to or exceeds b_n out of n patients with full toxicity follow-up (see table below). This is a Pocock type stopping boundary that assumes that a DLT rate of 0.30 is acceptable. If the true DLT rate is equal to 0.30, the probability of crossing the boundary is 0.20.

Number of Patients, n 1	2	3	4	5	6	7	8	9	10
Boundary, bn -	-	3	4	4	4	5	5	6	6
Number of Patients, n 11	12	13	14	15	16	17	18	19	20
Boundary, b _n 7	7	7	8	8	9	9	9	10	10
Number of Patients, n 21	22	23	24	25	26	27	28	29	30
Boundary, bn 10	11	11	11	12	12	13	13	13	14
Number of Patients, n 31	32	33	34	35	36	37	38	39	40

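### The research biopsy samples only image-positive lesions, so the promised lesion-level sensitivity and specificity of PET/MRI and PET/CT cannot be validly estimated; the stated timing of the biopsy also conflicts between sections

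*Combined protocol and SAP*

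**What the plan says.** Section 4.2.6 makes the performance of PSMA-PET/MRI relative to PSMA-PET/CT a secondary endpoint. Its first measure is "Rate of identification and delineation of DIL (e.g. sensitivity and specificity"), and the reference standard is given as "Compared to a gold standard of image-guided prostate biopsy". Section 7.2.3 is more definite about the cores: "This is a research only biopsy and will be used to evaluate the sensitivity and specificity of PSMA-PET/MRI vs PSMA-PET/CT".

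What is sampled is set out in 6.1.1.1.3 item 4: "The GTVs (i.e. DILs), will be biopsied as a joint effort between the treating radiation oncologist and a urologist", with two cores per GTV. Section 7.2.3 and footnote 10 of the time and events table (8.1) agree. The GTVs come from the images: PI-RADS v2 on MRI and 30% of SUVmax on PET (6.1.1.1.3 item 3). The same item adds: "An additional volume (GTV-union) is created from both GTVs". The contours also draw on other information, "including tumor localization in the diagnostic biopsy and physical exam [palpation". No section describes a core from prostate outside a GTV. Section 10.3 names no analysis comparing PET/MRI with PET/CT.

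On timing, 7.2.3 and footnote 10 tie the biopsy to fiducial placement. Section 6.1.1.1.1 places the fiducials 1-2 weeks before the PET/MRI, whereas footnote 6 places them during the CyberKnife phase. In 6.1.1.1.3, items 2 to 4 run from image fusion on the planning CT, through contouring, to biopsy.

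**The concern.** Sensitivity needs the reference result for lesions that the test missed, and specificity needs it for benign tissue that the test called negative. Here the reference result exists only where imaging was positive. Figures computed from these cores would mainly reflect which lesions were chosen for biopsy. Because 10.3 gives no analysis for 4.2.6, the wording of 4.2.6 and 7.2.3 is the only guide to what will be reported.

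Timing affects what the cores can mean. A core taken before the scan cannot have been aimed at a GTV which that scan defined. A core taken after months of ADT and 45 Gy may understate cancer and turn true lesions into apparent false positives. At stake is the credibility of one secondary endpoint. The primary toxicity test does not use these data.

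**Working it through.** The plan gives no precision or sample-size figure for 4.2.6, so there is nothing of its own to reproduce.

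**1. By construction.** Suppose the biopsied lesions are exactly the PET/MRI-positive ones. Then PET/MRI has no false negatives and no true negatives among lesions with histology. Apparent sensitivity is TP/(TP + 0) = 100% and apparent specificity is 0/(0 + FP) = 0%, whatever the true accuracy.

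**2. Patients with no core.** Section 10.2 says that the "dominant intraprostatic lesion (DIL, image-identified tumor in the prostate) can be safely defined in around 75% of the patients". At the planned enrolment, 42 x (1 - 0.75) = 10.5, so about 10-11 men with confirmed cancer would have no GTV and no core. Section 2.3 is more optimistic: "When looking at PSMA-PET defined DILs alone, the detection rates could be over 95" per cent, which gives 42 x (1 - 0.95) = 2.1, or about 2 men. None of these misses enters a biopsy-based sensitivity.

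**3. Size of the distortion (illustration).** Assumed true values are the slice-level figures in 2.3, used as lesion-level inputs:

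- PET/MRI: sensitivity 0.82, false-positive rate 1 - 0.67 = 0.33.
- PSMA-PET alone, standing in for PET/CT: sensitivity 0.75, false-positive rate 1 - 0.87 = 0.13.

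Both scans share one injection (2.4), so overlap is assumed to lie between halfway (midway from independence to nesting) and full nesting of PET/CT calls within PET/MRI calls.

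- Both positive, cancer: independence 0.82 x 0.75 = 0.615; nested 0.75; halfway 0.6825.
- Both positive, benign: independence 0.33 x 0.13 = 0.0429; nested 0.13; halfway 0.08645.

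*GTVs positive on either scan biopsied.* At halfway, the biopsied fraction of cancers is 0.82 + 0.75 - 0.6825 = 0.8875, and of benign sites 0.33 + 0.13 - 0.08645 = 0.3736. Apparent sensitivity is true sensitivity divided by the first. Apparent specificity is 1 minus the false-positive rate divided by the second.

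*Only PET/MRI-positive GTVs biopsied.* The biopsied fractions are 0.82 and 0.33. For PET/CT at halfway, apparent sensitivity is 0.6825/0.82 and apparent specificity is 1 - 0.08645/0.33.

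| Biopsy rule, overlap | PET/MRI sens / spec | PET/CT sens / spec | TP ratio | FP ratio |
|---|---|---|---|---|
| Assumed truth | 82% / 67% | 75% / 87% | 1.09 | 2.54 |
| Either scan, halfway | 92.4% / 11.7% | 84.5% / 65.2% | 1.09 | 2.54 |
| Either scan, nested | 100% / 0% | 91.5% / 60.6% | 1.09 | 2.54 |
| PET/MRI only, halfway | 100% / 0% | 83.2% / 73.8% | 1.20 | 3.82 |
| PET/MRI only, nested | 100% / 0% | 91.5% / 60.6% | 1.09 | 2.54 |

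The ratios are PET/MRI over PET/CT. They survive under the either-scan rule, but only if the cores are error-free.

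**4. Imperfect cores.** Assume half the candidate lesions are cancer, a core finds 70% of cancers, and core errors are unrelated to the scan result. Apparent false positives are then:

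- PET/MRI: 0.5 x 0.82 x 0.3 + 0.5 x 0.33 = 0.123 + 0.165 = 0.288.
- PET/CT: 0.5 x 0.75 x 0.3 + 0.5 x 0.13 = 0.1125 + 0.065 = 0.1775.

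The false-positive ratio becomes 0.288/0.1775 = 1.62 instead of 2.54. The true-positive ratio stays at 1.09.

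**5. Timing.**

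- Biopsy with fiducials, per 6.1.1.1.1: 1-2 weeks before the scan.
- Order of 6.1.1.1.3 items 2-4: after contouring on the planning CT, which 6.1.1.1.2 sets at roughly 8 weeks into ADT.
- Footnote 6 read literally: EBRT starts about 8 weeks after ADT (footnote 9) and CyberKnife about 6 weeks after that, so 8 + 6 = 14 weeks of continuing ADT, after 25 x 1.8 = 45 Gy.

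No section places the biopsy after the scan and before ADT.

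**The case against.** The strongest reply is that the endpoint is comparative. Section 4.2.6 offers sensitivity and specificity only as an example, both scans are to inform radiation design (2.4), and a relative comparison does not need image-negative cores. Part of this stands: positive predictive value is available for biopsied lesions, and ratios are available if GTVs positive on either scan were sampled. It does not rescue the wording, because 7.2.3 names sensitivity and specificity outright and 10.3 offers no other measure.

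A second reply is that the diagnostic biopsy could supply histology for image-negative tissue. It is not named as the reference for that purpose, and it informs the contours, so it is not independent of the calls being judged.

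Third, footnote 6 may be loose drafting. Section 6.1.1.1.1 puts the fiducials before radiation planning, and 6.1.1.1.3 item 2 needs them in place for registration. That is fair. A reader might infer that the cores will be taken after 45 Gy, but the documents support only a conflict between sections.

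Finally, the sizes rest on assumed inputs and on planned enrolment, while the current version supports early closure for low accrual. That also stands.

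**Conclusion.** The plan is wrong as written on this point. Cores from image-positive GTVs alone cannot give valid absolute lesion-level sensitivity or specificity for either scan. That follows from the sampling rule and needs no assumed numbers. The illustrated size, with PET/CT at 75%/87% appearing as 85-91%/61-65% under either-scan biopsy, does depend on the assumed accuracies, the PET-alone proxy, the overlap and error-free cores. The size of any timing effect is not known.

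Three stronger readings are tempting but not supported:

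- That PET/MRI will inevitably show 100%/0%. This holds if the biopsied set equals the PET/MRI-positive set, and the text does not say which scan supplies the PET contour.
- That no comparison of the scans is possible. Paired counts and positive predictive value remain, and ratios remain under the either-scan rule, subject to core error and to contouring informed by the diagnostic biopsy.
- That the safety conclusion is touched. Only secondary endpoint 4.2.6 is affected.

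A per-patient figure is possible, but every man has confirmed cancer (5.1.3). There is no per-patient specificity, and any call counts as correct wherever it falls, so the figure is a positivity rate.

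**What to change.** In 4.2.6 and 7.2.3, replace lesion-level sensitivity and specificity with:

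- paired 2x2 counts of PET/MRI and PET/CT calls, separately by biopsy result, and per-lesion positive predictive value;
- true-positive and false-positive ratios only if GTVs positive on either scan were biopsied, noting that missed cancer in the cores distorts the false-positive ratio and that contouring used the diagnostic biopsy;
- a per-patient DIL positivity rate for each scan, with all scanned patients as denominator, not labelled sensitivity.

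Record which scan supplied the PET contour, and the dates of scan, biopsy, ADT start and EBRT start. Exclude pre-scan biopsies from the accuracy table and show post-EBRT biopsies separately.

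The change needs wording and tabulation only, with no added procedure or visit. The price is that the absolute sensitivity and specificity figures are dropped and that few lesions may qualify, especially with early closure. It is still worth making, because 10.3 applies the same analysis plan to whatever data exist at termination.
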